5B.1. Project Life Force Clinical Intervention:

is a manualized, weekly 90-minute group treatment lasting 3 months coinciding with the time frame for enhanced monitoring of Veterans identified as “high-risk”. Session content is described in **Table 1**. The use of DBT skills⁹ in PLF differs from other DBT interventions in that it focuses primarily

on emotion regulation (ER), distress tolerance and interpersonal effectiveness *in the specific context of implementing a safety plan*. Mindfulness is not covered. PLF is augmented with additional skill modules on strengthening friendships and education pertaining to suicide risk, suicide means restriction and suicide prevention mobile Apps.

This is an open-group format, with new members joining throughout the 12-week cycle to allow immediate access to the skills and accommodate the need for expeditious safety planning for higher risk Veterans. While traditional DBT skills groups enter patients at designated points (e.g. the beginning of new skills modules), there is a growing evidence base of the effectiveness of DBT skills groups offered in more flexible frameworks, including drop-in formats¹⁵. Our open-group framework facilitates ease of entry. Since the program runs continuously, Veterans who join after session #1, can pick up any missed material in the next cycle. This project will randomize subjects over a one-year time frame to 12 weeks of either TAU or PLF. The study will include 4 cycles of the PLF intervention. See **Appendix 2** for PLF handouts and more detail on individual session lesson plans. PLF session format will be modeled after DBT skills groups and include: 1) brief check in and any follow up pertaining to use of the safety plan, 2) homework review, 3) teaching of new material and skill, 4) in-class practice of the skill, and 5) assignment of homework/ outside practice/development of safety plan.

5B.2. Finalize PLF manual: With input and feedback from co-investigators Drs. [name] (SSP original developer), [name] (clinical trial development, family interventions), [name] (DBT, psychotherapy engagement), [name] (health services, implementation) and [name] (PCC Director), the PI will finalize the PLF manual and associated handouts. We will also create a tool for assessing fidelity to PLF (see **5C.3.1**).

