5C. Phase 2, Randomized Clinical Trial: 40 suicidal Veterans will be randomized to PLF and TAU to examine the feasibility, acceptability and preliminary efficacy of PLF.

5C.1. Study Site. The study will recruit 40 suicidal Veterans over 1 year from the James J. Peters VAMC (JJPVA) (Bronx, NY). The JJPVA has functioned as the main site of recruitment for [name] study on suicidal behavior that recruited and *successfully assessed 324 suicidal Veterans* over the course of the study. The current proposal will benefit from the infrastructure already in place for recruitment of HR suicidal Veterans. JJPVA has a 30-bed psychiatric inpatient unit, an

average length of stay of 12 days and over 518 psychiatric admissions last year. Approximately 18% (n=82) of these admissions involved suicidal symptomatology, requiring the construction. Safety Plans prior to discharge. In addition, we will also recruit from outpatient clinicians and suicide prevention coordinators who have identified Veterans requiring a SSP; a strategy we used for our qualitative pilot study on safety planning (see **preliminary work**, section 4.1). We do not anticipate any difficulty recruiting 40 subjects across inpatient and outpatient services.

5C.2. Veteran Participants. 40 Subjects identified for use of a safety plan (e.g. discharged from inpatient hospitalization for suicidality, placed on the high-risk list, or outpatients who evidence increase in suicidality but not severe enough to warrant hospitalization) will be recruited for the study. Inclusion Criteria include: 1. Veterans ≥ 18 ; 2. Able to give consent; 3. Recent Suicidality and recommendation for a SSP initial construction or revision. Exclusion Criteria include: 1. Does not speak English. 2. Schizophrenia diagnosis. 3. Inability to tolerate group therapy format.

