5C.3. Experimental Condition- PLF. The pilot will use the PLF intervention finalized during Phase 1a of the proposed project. PLF is a 90-minute, 12 sessions, held weekly run by two clinicians using the final version manual and handouts from Phase 1a (see research plan, **5B.1**, and **appendix 2** for current version) with the stated purpose of developing, refining and implementing the SSP. The treatment is adjunctive and SSPs developed in the PLF Intervention will be shared with the Veteran's treatment team for feedback/approval. Veterans randomized to PLF will continue with their psychiatrist, case manager and services by the suicide prevention coordinator as indicated.

5C.3.1. PLF Training and Fidelity. Our research team (Drs. [name], [name], [name]) has experience developing psychosocial interventions and establishing their fidelity. Similar to our DBT RCT for suicidal Veterans (see **preliminary work**, section 4.2), PFL training will include weekly supervision with therapists and videotaping and review of sessions for fidelity using an objective scale. This adherence scale will be finalized with assistance by [name] during phase 1a of the project, and include ratings along a 5 point Likert scale (0- unacceptable, 5- excellent) assessing core features of the framework, content and principles of the treatment for each session along with competence variables including ability to manage the group, build rapport, manage crises. For the PLF RCT (phase 2), ratings will be performed by an independent rater on randomly selected group sessions. Overall ratings require an average score of 4 or above for adequate adherence to the intervention.

5C.4 Comparison Condition- TAU. The comparison condition, treatment as usual (TAU) will consist of the standard treatment delivered to suicidal Veterans in the VA including visits with the outpatient psychiatrist and case manager, with content of sessions and treatment appointment intervals determined by the subject's treatment team and suicide prevention coordinator's suggestions.

5C.5. Randomization Procedure. After the baseline assessment, participants will be informed of their assigned condition. Subjects will be assigned to study group using a blocked randomization plan with blocks of random sizes. Block sizes will be of either 2, or 4. The blocking will aid in keeping investigators blinded to study group assignment. A total of 20 Veterans are randomized to each group.

5C.6. Participant Assessment.

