5C.6.1. Subject Characterization (see Table 2).

1. Clinical Characteristics- Lifetime suicide attempts: Columbia Suicide History Form (CSHF) records lifetime suicide attempts & methods, including lethality, precipitant, and surrounding circumstances (5-10 minutes). The scale has inter-rater reliability of 0.97, and been used extensively in prospective suicide studies¹⁶.

2. Demographics: The study team will collect data via EHR- age; ethnicity, psychiatric treatment history, including medications; medical history; years of education; marital, housing and employment.

3. Diagnosis: It is well known that certain mental illnesses place individuals at high risk for suicide. These include MDD, bipolar disorder, borderline and antisocial personality disorders, substance abuse and schizophrenia. Diagnosis will be determined by chart review.

Table 2. Subject Characterization

Type of Data	Variables	Data Source
Diagnostic	Psychiatric diagnosis	Chart Review
Demographic	Age, sex, ethnicity, marital/family status, education, employment, housing status	Chart Review
Suicide History	Number of Suicide Attempts	Columbia Suicide History Form

5C.6.2. Measurement of Feasibility and Acceptability of PLF. To examine feasibility we will track participation, retention and dropout in PLF by measuring the number of session and specific sessions each Veteran attends, and clinician preparation and supervision time allocated to the intervention. For acceptability of PLF, participants will complete a brief survey (see **Appendix 3**) soliciting feedback upon completion of the PLF intervention at the 3-month assessment point.

5C.6.3. Efficacy Outcomes and Measures Overview. Veteran participants will be assessed in-person at baseline and at months 1, 3 and 6 (e.g. 3 months post intervention). These time points were specifically selected to allow us in order to collect information on the creation of the plan (baseline) and its use during the highest-risk period (first 4 weeks) and after acute symptom stabilization (12 weeks) (see **table 3**).

5C.6.3a. Primary Outcome Measure. Suicidal ideation will be measured using **The Beck Scale for Suicide Ideation (BSI)**¹⁷: 21-item self-report designed to assess severity of suicidal

attitudes and plans for suicide (5 to 10 minutes). It is based on the semi-structured interview, the Scale for Suicidal Ideation. BSI is internally consistent, high internal reliability (Cronbach α coefficients .87-.97)^{18,19} and moderate test-

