5D.4. Quantitative Analytic Strategy: Efficacy. We will first explore if any demographic features (e.g. gender, chart diagnosis) influence number of sessions attended and will include these demographic variables as covariates in our analyses where appropriate. The primary endpoint is self-reported suicidal ideation and secondary endpoints include self-reported measures of depression, hopelessness, reasons for living, and a treatment utilization measure of number of outpatient mental health visits attended. All of these metrics, except for treatment utilization, are continuous scales that will be measured at baseline and again at months 1, 3, and 6. For these outcomes, linear mixed models for longitudinal data²⁸ will be used for analysis. In these models, the fixed effects will be time, treatment group, and the interaction between time and treatment. The random effects will be the subjects. The interaction term in each model will test whether the trend in response over time differs between the treatment groups. The last secondary outcome, number of outpatient mental health visits attended, measures counts. A Poisson regression model will be fit to these data using Generalized Estimating Equations (GEE)²⁸ and the model will allow for testing whether the rate of outpatient visits for mental health differs between the two treatments. All statistical tests will be two-tailed with an alpha =.05.

For the Exploratory Aim, an Analysis of Covariance model with an interaction term will be used. In this model the outcome variable will be the CRIS-CAT score, the binary treatment variable will be whether the subject received PLF or TAU, the covariate will be the BSI, and the interaction will be that between the treatment variable and the Beck scale covariate. If there is no interaction, then the focus will be on the treatment effect. In this situation the regression lines relating CRIS-CAT to BSI will be parallel, and the treatment effect will measure the distance between the parallel lines providing a measure of the improvement in community integration over the entire range of the BSI in subjects receiving PLF compared to patients receiving TAU. On the other hand, if there is a significant interaction, this will correspond to a situation of intersecting regression lines for the two treatment groups. In such a circumstance, the improved community integration of one treatment group will be limited to a sub-range of the Beck scale.

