5D.5. Power and Sample Size Justification.

Although this is a pilot study with the purpose of investigating feasibility and collecting preliminary data to aid in planning a larger study, power calculations were carried out for the proposed sample size of 40 enrollees. With 20 subjects randomized to each of the two treatment groups, there will be 80% power to detect an effect size of 0.91. We recognize that this effect size is probably larger than the true effect size for these treatments, but one of the outcomes of this pilot trial will be the data allowing us to improve the required sample size estimates for a future study.

Figure 2--Study Time Line

6) Time Line. (See Figure 2)

RCT Recruitment is ongoing and Veterans can enter at any point during the RCT. During this time frame, we expect to recruit 4-5 Veterans/month from both inpatient and outpatient services.

activity	Month 1-6		Month 7-12		Month 13-18		Month 19-24	
Hire/train staff								
Finalize Manual & Obtain IRB approval								
Conduct RCT								
Conduct follow-ups								
Data analysis/papers

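### Recently hospitalized Veterans and non-hospitalized outpatients are randomized together without stratification or a source term in the model, which leaves a 40-person trial open to conditional bias and lost precision if source predicts change in BSI

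*Combined protocol and SAP*

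**What the plan says.** Section 5C.2 gives as examples of eligible Veterans those "discharged from inpatient hospitalization for suicidality, placed on the high-risk list, or outpatients who evidence increase in suicidality but not severe enough to warrant hospitalization". The expected split between inpatient and outpatient recruits is not stated.

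Section 5C.5 says that "Subjects will be assigned to study group using a blocked randomization plan with blocks of random sizes", that "Block sizes will be of either 2, or 4", and that "A total of 20 Veterans are randomized to each group". No stratification factor is named.

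Table 2 lists diagnosis, demographics and number of suicide attempts. It does not list recruitment source or high-risk-list status.

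Section 5D.4 fits a linear mixed model with fixed effects for time, treatment group and their interaction; the interaction is the efficacy test. Covariates may enter where appropriate, but the rule is for demographic features that influence the number of sessions attended. Section 5D.1 compares baseline characteristics between arms and states no consequence if they differ.

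**The concern.** The two main routes into the trial differ in the severity of the current episode by definition: one required admission and the other did not. If they also differ in how BSI changes over six months, a chance excess of one route in one arm moves the time-by-treatment interaction, which is the quantity tested. The movement could resemble a PLF effect or mask one.

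Blocking equalizes the arm sizes, not the mix of sources within them. The provisions already in the plan do not close the gap:

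- The covariate rule concerns demographics and is triggered by attendance, which is observed after randomization.
- A covariate entered only as a main effect would not correct the interaction; a source-by-time term is needed.
- Baseline BSI is one of the modelled time points, so a difference in starting level is handled. A difference in slope is not.

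The stake goes beyond the pilot's own test, because 5D.5 intends the data to improve the sample-size estimates for a future study.

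**Working it through.** **Inputs from the documents.** 40 Veterans, 20 per arm, blocks of 2 or 4 (5C.5); two-sided alpha 0.05 (5D.4); 80% power at effect size 0.91 (5D.5).

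**Assumed inputs.** The inpatient share, taken as about half, with 25% to 70% as a range. D, the difference between sources in mean BSI change, in units of the within-source SD of change, from 0.3 to 1.0. The documents give neither.

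**1. The plan's own figure.** Section 5D.5 states: "With 20 subjects randomized to each of the two treatment groups, there will be 80% power to detect an effect size of 0.91". A two-sample t-test with n = 20 per arm, d = 0.91 and two-sided alpha 0.05 has power 80.1%. The figure reproduces. The standard error of the contrast on this scale is √(1/20 + 1/20) = 0.316, about 0.32 SD.

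**2. Chance of imbalance.**

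- Each Veteran independently an inpatient with p = 0.5: the difference in inpatient counts plus 20 follows Binomial(40, 0.5). P(count gap ≥ 4, i.e. ≥ 20 points) = 26.8%; P(count gap ≥ 6, i.e. ≥ 30 points) = 8.1%. At p = 0.3 or 0.7 the values are 22.6% and 5.6%.
- Exactly 20 inpatients among 40: the number X in one arm is hypergeometric. P(|X − 10| ≥ 2) = 34.3%; P(|X − 10| ≥ 3) = 11.3%. With the inpatient total fixed between 25% and 70% of the 40, the ranges are 27–34% and 6.5–11%.

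The SD of the gap is nearly the same at one half: √(40 × 0.25)/20 = 0.158 in the first case and 0.160 in the second. The probabilities differ mainly because a fixed total of 20 allows only even count gaps. Simulating the stated blocks with exactly 20 inpatients gives 34.7% and 11.3%, so the blocking does not reduce the risk.

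**3. Shift in the contrast.** Shift = gap × D.

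| Gap in inpatient share | D = 0.3 | D = 0.5 | D = 1.0 |
|---|---|---|---|
| 20 points (12 v 8) | 0.06 SD | 0.10 SD | 0.20 SD |
| 30 points (13 v 7) | 0.09 SD | 0.15 SD | 0.30 SD |

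**4. Effect on the test, given a 30-point gap** (simulated comparison of change scores, no source term):

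| | D = 0.3 | D = 0.5 | D = 0.8 | D = 1.0 |
|---|---|---|---|---|
| Type I error | 5.4% | 6.8% | 9.0% | 10.3% |
| Power at 0.91, gap against PLF | 70% | 62% | 48% | 38% |
| Power at 0.91, gap favouring PLF | 86% | 89% | 93% | 94% |

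**5. Averaged over all randomizations.** Unadjusted type I error stays at about 5% for every D. Unadjusted power at 0.91 is 80.2% (D = 0), 77.8% (0.5), 73.8% (0.8) and 70.2% (1.0).

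**6. With the fix.** Stratified blocks bring the SD of the gap down to 0.02–0.04, and no simulated allocation reached 20 points. With source balanced and in the model, one residual degree of freedom is lost (38 to 37) and power is 80.0%. The gain is 80.0 − 77.8 = 2.2 points at D = 0.5 and 80.0 − 70.2 = 9.8 points at D = 1.0. At D = 0 power is about 80% either way. Adjustment without stratification averages about 79% and holds type I error near 5% at every gap simulated.

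**The case against.** The strongest objection is that the mechanism is not documented. No section gives a BSI course by source. A reader might infer from 5C.6.3, which times visits to capture safety-plan "use during the highest-risk period (first 4 weeks) and after acute symptom stabilization (12 weeks"), that recent inpatients start high and fall steeply while outpatients change less. That passage explains the visit schedule for all participants. Veterans already discharged may have passed their peak by baseline, and outpatients are referred because suicidality has increased and may themselves regress. This stands: D and its direction are assumptions.

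A reader might also infer that the arms would receive different monitoring, because 5B.1 describes the three months of PLF as "coinciding with the time frame for enhanced monitoring of Veterans identified as" high-risk. The text does not say that such monitoring is confined to those Veterans, and it gives no difference by source. Nor does 5C.2 describe the outpatients as never admitted: only the current episode did not warrant hospitalization, and high-risk-list status can overlap both routes.

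It is also fair to say that the confidence interval already allows for chance imbalance, that other prognostic factors could be argued for, that psychiatric treatment history is collected from the record (5C.6.1), and that this is a pilot whose authors concede 0.91 is probably too large. These points limit the severity. They do not remove the case for using one baseline factor that is known at entry, that the eligibility criteria themselves tie to severity, and that costs almost nothing to include.

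**Conclusion.** The point holds as a matter of conditional bias and precision. It would be wrong to read it as a flaw in the validity of the randomization or as inflated overall type I error, which stays at about 5%.

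With about half of the sample recently hospitalized, a gap of at least 20 points arises in 27% to 34% of randomizations and one of at least 30 points in 8% to 11%. The resulting shift is modest when D is 0.5 or less: 0.15 SD or under at a 30-point gap, less than half a standard error. It approaches one standard error (0.30 against 0.32 SD) only at D = 1.0. The average power loss runs from about 2 points at D = 0.5 to about 10 at D = 1.0. All of these sizes rest on the assumed D and inpatient share and on a change-score approximation to the mixed model. The change is worth making before enrollment, since stratification cannot be added afterwards.

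**What to change.** 1. In 5C.5, stratify the blocks by one binary factor fixed at entry: enrolled on discharge from the current hospitalization for suicidality, v all others. Classify high-risk-list Veterans by the same rule.
2. In Table 2, add recruitment source, taken from chart review.
3. In 5D.4, prespecify source and source-by-time as fixed effects in the mixed model, whatever the baseline comparison shows.
4. In 5C.5, change the statement of 20 Veterans per group to approximately 20.

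The cost is a second randomization list, one chart-review field and a few sentences. Each stratum can stop halfway through a block of 4 with an imbalance of 2, so the arms may end at 21 v 19 or at most 22 v 18. The model spends two degrees of freedom if time is linear (source, source × time), or four if the four visits are categorical (one for source, three for source × time); 5D.4 does not say which. The power cost is negligible if source turns out not to be prognostic.

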Table 3. Clinical Assessment Measures and Schedule

Outcome	Measures	Baseline	Month 1	Month 3	3 Months follow-up
Primary: Suicidal ideation	Beck Scale for Suicidal Ideation (BSI)	X	X	X	X
Secondary: Hopelessness/ Depression	Beck Hopelessness Scale (BHS)	X	X	X	X
	Beck Depression Inventory (BDI)	X	X	X	X
Reasons for living	Reasons for Living Scale	X	X	X	X
Outpt MH Treatment utilization	Count of CPRS mental health visits in previous 90 days	X			X
Exploratory: Community reintegration	Computer Adaptive Test version of the Community Reintegration of Injured Service Members measure	X	X	X	X

retest reliability ($r=.54$)²⁰. A principal factor analysis identified 3 factors for the BSI: desire for death, preparation for suicide and actual suicide desire¹⁵.

5C.6.3b. Secondary Outcome Measures: proximal psychosocial outcomes include depression, hopelessness, reasons for living, and outpatient mental health treatment utilization.

Beck Depression Inventory-II (BDI-II)²¹ consists of 21 items related to symptoms of depression and is scored based on a Likert scale. Widely used in adults and adolescents, it has high internal consistency (Cronbach coefficient $\alpha = .92$).

The Beck Hopelessness Scale (BHS)²² is a 20-item self-report measure with true-false items that assess hopelessness and the extent of positive and negative beliefs about the future. Adequate reliability and concurrent validity data exist for this measure²³.

The Reasons for Living Inventory (LRFL)²⁴ is a 48-item self-report measure with 6 subscales: Survival and Coping Beliefs (24 items), Responsibility to Family (7 items), Child-Related Concerns (3 items), Fear of Suicide (7 items), Fear of Social Disapproval (3 items), and Moral Objections (4 items). These beliefs and expectations about not dying by suicide are rated on a 6-point Likert scale. The LRFL has high internal reliability and good test-retest reliability²⁵.

Outpatient Mental Health Treatment Utilization: Using CPRS we will count the number of outpatient mental health visits attended by participants prior to the intervention and compare to the number of outpatient visits attended 3 months post intervention.

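### Section 5D.4 leaves the baseline group difference free and does not adjust for baseline score, so a valid test gives up precision in a randomised trial of 40

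*Combined protocol and SAP*

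**What the plan says.** Section 5D.4 describes the primary endpoint (BSI) and the secondary scales (BHS, BDI-II, Reasons for Living) as "continuous scales that will be measured at baseline and again at months 1, 3, and 6". For these it fits linear mixed models: "In these models, the fixed effects will be time, treatment group, and the interaction between time and treatment". It adds: "The random effects will be the subjects". The interaction is the test, described as a test of whether the trend over time differs between groups. The section does not say whether time is linear or categorical, and it names no primary visit. The only covariates mentioned are demographic features.

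Other relevant text:
- Section 5C.5: "A total of 20 Veterans are randomized to each group". Participants learn their assignment after the baseline assessment.
- Section 5D.1 compares the groups at baseline by chi-square and t-tests, with no stated consequence for the model.
- Section 5D.2 uses direct likelihood on all available data.
- Section 5D.5: "With 20 subjects randomized to each of the two treatment groups, there will be 80% power to detect an effect size of 0.91".
- Section 5C.6.3a reports a published BSI test-retest reliability of .54. It is the only BSI correlation across time in the documents, and the power statement does not refer to it.

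**The concern.** Randomisation makes the two true baseline means equal. A model with a free group effect, and with baseline among the responses, nevertheless estimates a baseline difference. It then measures treatment relative to that difference: as a difference in change from baseline if time is categorical, or as a difference in slope if time is linear. When baseline and follow-up are imperfectly correlated, full subtraction adds noise that a common baseline mean, or baseline as a covariate, would avoid.

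With 20 per arm this is not negligible. The chance difference in baseline means has a standard deviation of √(2/20) = 0.32 baseline SD. Under normality, a gap above 0.25 SD in either direction has probability of about 43% (0.25/0.316 = 0.79).

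Precision is scarce here. Section 5D.5 concedes that the detectable effect probably exceeds the true one, and says the data will inform the sample size of a later study. A needlessly noisy estimate would carry into that planning.

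**Working it through.** **Inputs.** From the documents: 20 per arm (5C.5); visits at months 0, 1, 3 and 6; fixed and random effects as in 5D.4; "All statistical tests will be two-tailed with an alpha =.05". Assumed: a random intercept (equal correlation r between any two visits), equal variances, complete data, and r = .54 as a stand-in with a range of .3 to .8. Units are raw-score SDs. Loss means 1 − Var(common baseline mean)/Var(free baseline difference).

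**The plan's own figure.** A two-sample t-test with 38 df and noncentrality 0.91 × √(20/2) = 2.88 gives 80.1% power; the detectable effect at 80% is 0.909. The stated power therefore reproduces as an unadjusted comparison of two means (variance factor 1.00), not as a calculation for the planned interaction.

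**One follow-up visit, categorical time.**
- Free: 4(1 − r)/n = 4 × 0.46/20 = 0.0920, SE 0.303.
- Common baseline or covariate: 2(1 − r²)/n = 2 × 0.7084/20 = 0.0708, SE 0.266.
- Ratio (1 + r)/2 = 0.77, a loss of 23%. The detectable difference falls from 0.87 to 0.77 SD. Matching the adjusted precision would take 40/0.77 ≈ 52 Veterans.

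**Linear slope.** For t = (0, 1, 3, 6), Σ(t − 2.5)² = 21, Σt² = 46 and (Σt)² = 100.
- Free: information per arm 21/(1 − r) = 21/0.46 = 45.65.
- Common intercept: [46 − 100r/(1 + 3r)]/(1 − r) = (46 − 20.61)/0.46 = 55.19.
- Ratio 45.65/55.19 = 0.83, a loss of 17%.

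**Average of months 1, 3 and 6.**
- Free: (2/n) × 4(1 − r)/3 = 0.1 × 0.6133 = 0.0613.
- Common baseline: (2/n) × (1 − r)(1 + 3r)/3 = 0.1 × 0.4017 = 0.0402.
- Ratio (1 + 3r)/4 = 0.655, a loss of 34.5%.

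| r | Linear trend | One visit | Follow-up average |
|---|---|---|---|
| .3 | 30% | 35% | 52.5% |
| .54 | 17% | 23% | 34.5% |
| .7 | 10% | 15% | 22.5% |
| .8 | 7% | 10% | 15% |

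**Joint 3-df interaction test, categorical time, r = .54.** The loss in noncentrality depends on the effect's shape: 17% if it grows linearly to month 6, 34.5% if it is full from month 1 onward, and 26% to 28.5% for two intermediate patterns.

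**Against the stated 80%: one-visit power at 0.91 SD.**

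| r | Free baseline difference | Baseline-adjusted |
|---|---|---|
| .3 | 66% | 84% |
| .4 | 73% | 86% |
| .5 | 80% | 90% |
| .54 | 83% | 91.5% |

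**The case against.** The planned model is a standard longitudinal model. Under randomisation its estimate is unbiased and its test is valid. Full subtraction of a chance imbalance misleads only conditionally on the imbalance observed. This is a pilot whose stated purpose is feasibility and planning data. All of that stands, and it makes the point one of efficiency, not of error.

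The size is also uncertain. The value .54 is a published reliability, not a baseline-to-follow-up correlation in these patients, and no such number is given for the other three scales. Veterans enter on recent suicidality, so baseline and follow-up variances may differ. Complete data is optimistic: section 4.2 reports that 59% completed six months in the team's earlier trial. These objections limit the figures but do not reverse the direction. For one visit, let k be the ratio of baseline to follow-up SD. The change variance exceeds the adjusted variance by (1 + k² − 2rk) − (1 − r²) = (k − r)², which is never negative, apart from the small cost of estimating the adjustment.

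That baseline belongs to the outcome vector is inferred from the list of measurement times and the absence of a baseline covariate. It is the natural reading, but section 5D.4 does not say so outright.

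A reader might infer that the plan tests change scores and forfeits a fixed 23%. The documents do not support that: the section speaks of a trend, leaves the coding of time open, and supplies no correlation for the purpose. A reader might also infer that the power statement is wrong. It reproduces as an unadjusted comparison, and at r = .54 the one-visit change contrast does slightly better (variance factor 0.92 against 1.00). A shortfall arises only if r is below .5.

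**Conclusion.** The concern holds as a loss of precision. On the natural reading, 5D.4 leaves the baseline group difference free and makes no use of baseline score as an adjuster, in a randomised trial where 20 per arm makes chance imbalance likely. At the stand-in r = .54 the cost is roughly one sixth to one third of the variance, depending on which contrast the interaction represents. It shrinks as r rises, and was positive for each contrast at every r checked from .3 to .8.

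These sizes rest on a random intercept, equal variances and complete data, and should be quoted as a range. Nothing here shows bias, an invalid test or a contradiction of the stated power. The unstated time coding and primary contrast are part of the same gap, because the size of the loss cannot be fixed without them.

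**What to change.** In 5D.4, for BSI, BHS, BDI-II and Reasons for Living:

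1. Keep baseline in the outcome vector and constrain the two arms to a common baseline mean. That is, drop the treatment main effect at baseline, with time coded so that baseline is zero or the reference level.
2. State whether time is linear or categorical, and name the primary contrast (slope difference, a named visit, or the follow-up average).

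This form retains Veterans who have only a baseline assessment, in line with the direct-likelihood approach in 5D.2.

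The alternative is to model months 1, 3 and 6 with baseline score as a covariate. The tested term must then become the treatment effect at follow-up, at a named visit or averaged. If the interaction stayed the test, it would compare trends only from month 1 to month 6 and miss an effect already present at month 1. This version also drops Veterans with baseline only, so the common-baseline form is preferable.

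The cost is a few sentences in 5D.4, settled before outcome data by arm are examined. No extra visits, measures or patients are needed.
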